6.1.2. Statistical Hypotheses

For each of the **sector of the mean change** implant treatment groups, the primary efficacy objective for this study is to demonstrate that the mean change from baseline in diurnal IOP in the study eye is not inferior to the mean change from baseline in diurnal IOP in the timolol group at 8AM and 10AM at each of Day 10, Week 6, and Month 3 visits (6 timepoints).

The primary analyses will compare each of the implant treatment groups to the control treatment group with respect to the mean change from baseline in IOP at each of the 6 timepoints.

To control the overall type I error at 0.05 level for comparing the two testing arms to Timolol,

6.1.3. Handing of Missing Data/Intercurrent Events for Efficacy Variables

The approaches listed below will be used for handling missing data/intercurrent events:

- Observed Case (OC): Missing data are not imputed. Only subjects with available data at the given time point are considered. No special handling for intercurrent events. OC will be the secondary approach for sensitivity analysis of primary and secondary efficacy endpoints.
- Last Observation Carried Forward (LOCF): The LOCF analyses will use the last observed non-missing, time consistent, evaluation for efficacy measures assessed to impute missing data at later visits. Baseline efficacy evaluations will not be carried forward. No special handling for intercurrent events. LOCF will be the secondary approach for sensitivity analysis of primary endpoints.
- Non-Responder Imputation (NRI): Subjects who have missing data or intercurrent events at the timepoint of interest are treated as though they did not respond to the treatment. NRI will be applied to the responder analyses.

6.1.4. Multiplicity Adjustment

6.1.5. Primary Analysis

The analysis of covariance (ANCOVA) model with change from baseline in IOP at the given visit (Day 10, Week 6, and Month 3) and timepoint (8AM, 10AM) as the response, treatment as a main effect factor, will be applied for each timepoint of each visit separately. Point estimates and corresponding 95% confidence intervals will be provided for the difference between the G2-TR at two different elution rates versus Timolol group (G2-TR – Timolol).

6.1.6. Sensitivity Analyses

To evaluate the robustness of the primary analysis results, the following sensitivity analyses of the primary efficacy endpoints will be performed, including different imputation methods for missing data:

1. Sensitivity Analysis 1

2. Sensitivity Analysis 2

3. Sensitivity Analysis 3

4. Sensitivity Analysis 4

5. Sensitivity Analysis 5

Similar to the primary analysis, an ANCOVA model will be performed for the ITT analysis set on observed case (OC).

6. Sensitivity Analysis 6

Similar to the primary analysis, an ANCOVA model using the last observation carried forward (LOCF) method described in Section 6.1.3 will be performed for the ITT analysis set.

6.1.7. Summary of Planned Analyses

[1] ANCOVA model including treatment as the main effect for the first of the first

6.1.8. Subgroup Analyses

Subgroup analyses will be performed for the primary efficacy endpoint in the ITT analysis set with the . The subgroups are defined as follows:

- Age (<65 vs. \geq 65)
- Sex (Male vs. Female)
- Race (White vs. Non-White)
- Type of disease (OAG vs. OHT)
- Baseline mean diurnal IOP

The primary efficacy endpoint will be summarized separately for each subgroup to evaluate

	-
.   2	

		2
	Į	

7. Safety Analyses

The safety analyses will be based on the safety analysis set.

7.1.1. Extent of Exposure

Duration of exposure to study treatment in days will be calculated using the study exit date – surgery date + 1. If the study exit date is missing for subjects with early termination, then the date of last visit will be used as the study exit date. Study duration will be summarized as continuous variable by treatment group for the Safety analysis set. A subject listing will be provided.

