### 4 STUDY DESIGN

This is a prospective, randomized, double-masked, active-controlled, parallelgroup, multi-center clinical trial comparing the efficacy and safety of the Model G2TR Travoprost Intraocular Implant and the Model G2TR Travoprost Intraocular Implant to topical timolol in subjects with OAG or OHT. Approximately 558 subjects will be randomized in this study and will be followed through 3 years postoperative.

| CLINICAL FROTOCOL |               |               |  |
|-------------------|---------------|---------------|--|
| Date:             | Phase:        | Protocol No.: |  |
| June 06, 2022     | Phase 3 Study | GC-010        |  |

CUNICAL DROTOCOL

Screening Procedure:

After providing informed consent, prospective subjects will be evaluated against the screening criteria.

Subjects who qualify at Visit 1 (Screening) and have not used topical ocular hypotensive medications prior to Visit 1 (Screening) or who were on a topical ocular hypotensive medication but have stopped for the length of time in the washout schedule below do not require a washout period and may be scheduled for Visit 2 (Baseline) (on a separate day).

Subjects who qualify at Visit 1 (Screening), that were previously on a topical IOP lowering medication , but discontinued prior to Visit 1 (Screening) and are still within the protocol defined washout period will continue the medication washout according to the schedule below and will have Visit 2 (Baseline) scheduled to occur after the washout is completed.

Subjects who qualify at Visit 1 (Screening) and are using any topical IOPlowering medication in either eye will undergo medication washout according to the schedule below and Visit 2 (Baseline) will be scheduled to occur after the washout is completed.

If both eyes qualify at Visit 1 (Screening), the investigator may choose to implement a bilateral washout according to the following schedule:

Following the required washout period, subjects will return for Visit 2 (Baseline). The mean diurnal IOP measured at Visit 2 (Baseline) must be In addition, the and the IOP at each timepoint (8AM, 10AM, and 4PM) is in the study eye, in addition to all other entry criteria. The investigator will then designate the qualified eye as the study eye; if both eyes qualify, the RIGHT eye will be selected as the study eye. The subject may then be scheduled for study treatment. Subjects will be treated unilaterally, only one eye will go through the study treatment

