9.	Changes to Protocol-planned Analyses	42
10.	Supporting Documentation	43
11.	References	45

List of Abbreviations

AE	Adverse Event
ANCOVA	Analysis of Covariance
BSCVA	Best Spectacle Corrected Visual Acuity
C/D	Cup-to-Disc
CI	Confidence Interval
COV	Coefficient of Variation
CRF	Case Report Form
dB	Decibels
ECD	Endothelial Cell Density
ETDRS	Early Treatment of Diabetic Retinopathy Study
ICE	Intercurrent Events
IOP	Intraocular Pressure
ITT	Intent-To-Treat
LogMAR	Logarithm of the Minimum Angle of Resolution
MAR	Missing At Random
MedDRA	Medical Dictionary for Regulatory Activities
MI	Multiple Imputation
MCMC	Monte Carlo Markov Chain
MNAR	Missing Not At Random
mmHg	Millimeters of Mercury
NRI	Non-Responder Imputation
OAG	Open-Angle Glaucoma
OC	Observed Case
OHT	Ocular Hypertension
PI	Principal Investigator

РР	Per-Protocol Analysis set
РТ	Preferred Term
SAE	Serious Adverse Event
SOC	System Organ Class
TEAE	Treatment Emergent Adverse Event
VA	Visual Acuity
VF	Visual Field

Version History

This Statistical Analysis Plan (SAP) for GC-010 is based on the protocol dated on 06JUN2022.

SAP Version	Approval Date	Change	Rationale
1.0	19MAY2022	Original Version	
2.0	09JUN2022		

1. Introduction

This Phase 3 study evaluates the safety and efficacy of two intraocular implants that elute travoprost at different rates in subjects with open-angle glaucoma (OAG) or ocular hypertension (OHT). The study duration is 36 months postoperative. Two database locks, Month 12 and Month 36, are planned. The primary efficacy evaluation is based on IOP data collected in the first three months after the first dose; key secondary efficacy evaluation is based on Month 12 data.

The primary database lock will occur after all subjects have completed the 12-month visit or prematurely discontinued prior to that time. At that time, the randomization code will be unmasked to the project team after all the data queries related to the efficacy and safety outcomes are resolved and corresponding data revisions are completed in the database. To prevent bias and to maintain data integrity, study subjects and the PI and site study personnel will remain masked through Month 36.

This statistical analysis plan provides details of the planned analyses to be performed at the time of the Month 12 and Month 36 database lock. Shells of tables, listings and figures are presented in a separate document.

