2.2. Study Design

This is a prospective, randomized, double-masked (subject and observer), active-controlled, parallel-group, multicenter trial comparing the efficacy and safety of the Model G2-TR-063 Travoprost Intraocular Implant and the Model G2-TR-125 Travoprost Intraocular Implant to topical Timolol in subjects with OAG or OHT. A total of approximately 558 males and females \geq 18 years of age who were diagnosed with OAG or OHT will be randomized to one of three treatment arms in a 1:1:1 allocation:

- G2-TR-063: Travoprost Intraocular Implant, high elution rate (Model G2-TR-063), with placebo eye drops.
- G2-TR-125: Travoprost Intraocular Implant, low elution rate (Model G2-TR-125), with placebo eye drops..
- Concurrent Control: Sham surgery with Timolol Maleate Ophthalmic Solution, USP, 0.5% (timolol).

The randomization will be stratified into two groups based on baseline mean diurnal IOP

Subjects are required to meet all eligibility criteria at the Screening visit. If the subject is using ocular hypotensive medications at this visit, she/he is required to complete the appropriate medication washout period listed below before returning for the Baseline visit; subjects who are not using hypotensive medication may be scheduled for a Baseline visit (on a separate day).

is

in the study eye after medication washout period.

Following completion of the baseline visit, eligible subjects are scheduled for the operative examination. At this visit, subjects will be randomized to treatment and per randomized assignment, either implanted with G2-TR-063, G2-TR-125, or have the sham surgical procedure performed.

Follow-up visits are scheduled at postoperative Day 1-2, Day 10, Weeks 4, 6, Month 3 and every 3 months thereafter through Month 36.

Postoperatively, for the duration of the study, subjects in the G2-TR-063 and G2-TR-125 arms are instructed to use placebo eye drops (artificial tears) twice daily in the study eye, while subjects in the control arm, following sham surgery, are instructed to instill topical timolol 0.5% eye drops, solution twice daily in the study eye. The investigator could administer or prescribe ocular hypotensive medication at a first or later after the operative exam based on the IOP values, please refer to the Figure 3 in the protocol for post-treatment management of IOP and rescue medications.

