2.3. Assessment Schedule

2.4. Sample Size Determination

In order to detect adverse events that occur at a rate of 1% or higher, safety in the clinical program will be demonstrated in a minimum of 300 subjects who have completed the expected duration of drug elution from either implant model.

3. Analysis Sets

Intent to Treat Analysis Set (ITT)

This analysis set includes all subjects who are randomized.

Per-Protocol Analysis Set (PP)

The Per-Protocol analysis set is a subset of the ITT analysis set. It includes all the ITT subjects who received the study treatment based on the randomization schedule and do not have major protocol deviations likely to impact the primary efficacy endpoints.

Safety Analysis Set

The safety analysis set will contain all subjects who are randomized and receive at least one dose of study treatment. Subjects will be grouped according to their actual treatment received,

4. General Statistical Considerations

Continuous data will be summarized with the number of non-missing values, mean, standard deviation, minimum, median, and maximum. Other selected percentiles, such as the 25th percentile and 75th percentile may be presented for parameters that are not normally distributed or are suspected of exhibiting that tendency. Categorical data will be summarized with the number of non-missing values and the numbers of values equal to each of the possible values. Percentages of subjects with each of the possible values will be calculated from the number of subjects in the relevant cohort of the corresponding analysis set, unless stated otherwise. Some continuous variables may also be grouped into categorical levels and evaluated in frequency tables.

All inferential statistical analyses will be performed with a two-sided confidence level of 95% or a two-sided significance level of 0.05, except when stated otherwise using SAS[®] software, Version 9.4, or higher.

Data displays produced for this study will include three types: summary tables, data listings, and figures.

Data listings will simply list the data recorded on the case report form (CRF) or derived for each subject. They will be ordered by treatment, subject number, study eye, and time of assessment. Additional levels of ordering may be employed as appropriate. Data listings will not display subject initials.

In general, summary tables will be presented by treatment group:

- Implant
- Implant
- Sham/Timolol

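### Does SAP 7.1.1 need a new exposure definition because subjects still in follow-up at the Month 12 lock have no end date and the variable carries two names?

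*SAP*

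**What the plan says.** SAP 7.1.1 (Extent of Exposure) defines one variable: "Duration of exposure to study treatment in days will be calculated using the study exit date", minus the surgery date, plus 1. It has one fallback: "If the study exit date is missing for subjects with early termination, then the date of last visit will be used". It then states: "Study duration will be summarized as continuous variable by treatment group for the Safety analysis set". No second formula is given, so exposure and study duration appear to be the same quantity. The paragraph reads as complete, with no visible redaction.

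The SAP Introduction says the document covers "planned analyses to be performed at the time of the Month 12 and Month 36 database lock". The first lock comes once every subject has either completed the 12-month visit or discontinued before it. The project team is unmasked at that lock, while "study subjects and the PI and site study personnel will remain masked through Month 36". Protocol section 4 says subjects "will be followed through 3 years postoperative", and SAP 2.2 schedules visits at "Month 3 and every 3 months thereafter through Month 36".

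**The concern.** A subject who is past Month 12 but not yet at Month 36 when the first lock occurs has no exit date and is not an early termination. Neither branch of the rule covers that subject. Applied literally at Month 12, the table would describe only people who had already left or finished, which is not the Safety analysis set it claims to summarise. If the gap were noticed only after the lock, the end date might be chosen by a team that had been unmasked.

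The label raises a second doubt. The formula measures surgery to study exit and has no treatment-stop date. For a subject who stopped the drops but stayed in follow-up, the figure would overstate time on treatment. For the implant arms, time in study is also not the drug-elution period, and SAP 2.4 ties a safety target to that period: "safety in the clinical program will be demonstrated in a minimum of 300 subjects who have completed the expected duration of drug elution". A reader might take a table headed exposure as evidence on that target.

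**Working it through.** The plan states no figure for this variable, so there is nothing to reproduce. The check has three parts.

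**1. Is a rule given elsewhere?** In the readable text, SAP 4.1.3 defines study day only, 4.2 assigns data to nominal visits, 4.4.2 imputes adverse event and medication dates only, and 5.1 uses Months 3, 12 and 36 for exit status only. None supplies an end date for a continuing subject. The table shells are a separate document that was not available, so a rule there cannot be excluded.

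**2. How large is the gap?** The documents give 558 subjects, Month 12 and Month 36 locks, and visits every 3 months. Accrual and dropout are not given. Assume uniform accrual over A = 24, 36 or 48 months, yearly dropout d = 5, 10 or 15% at a constant hazard, and follow-up at the lock uniform from 12 to 12 + A months. A subject has no value if still in the study and short of Month 36. With λ = −ln(1 − d) per year:

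P(no value) = (24/A) × [(1 − d) − (1 − d)³] / (2λ)

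- A = 24, d = 5%: (0.95 − 0.857375) / (2 × 0.051293) = 0.903, and 558 × 0.903 = 504.
- A = 24, d = 15%: (0.85 − 0.614125) / (2 × 0.162519) = 0.726, and 558 × 0.726 = 405.

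| Accrual (months) | No value, of 558 | Literal mean (days) | Mean to data cutoff (days) |
|---|---|---|---|
| 24 | 405 to 504 | 368 to 388 | 618 to 692 |
| 36 | 270 to 336 | 691 to 914 | 701 to 801 |
| 48 | 202 to 252 | 761 to 961 | 743 to 855 |

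The literal mean is wrong by between −305 days (A = 24, d = 5%) and +114 days (A = 36, d = 5%). These two differences come from unrounded means.

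Nobody would issue that table: its N would fall short by at least 202 of 558, or 36%. The relevant size is the spread between sensible ways of filling the gap. With visits 3 months (about 91.3 days) apart, a continuing subject's last visit falls on average 91.3/2 = 45.7 days before a calendar cutoff. The shift in the mean is 45.7 × (number with no value)/558:

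- largest: 45.7 × 504/558 = 41 days
- smallest: 45.7 × 202/558 = 17 days

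If the Month 12 analysis instead cuts each subject at Month 12, take 186 per arm, exits spread evenly over days 1 to 365 (mean 183) and everyone else at 366 days:

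- 5% exited: (9 × 183 + 177 × 366)/186 = 357 days
- 10% exited: (19 × 183 + 167 × 366)/186 = 347 days
- 20% exited: (37 × 183 + 149 × 366)/186 = 330 days

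That cut answers a different question, and a table footnote would say which was used. Each convention depends only on dates, not on treatment.

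**3. Is time in study the wrong measure of exposure?** Protocol 7.3.1 sets the treatment period at three years. The Synopsis and Protocol sections 4 and 8 have the masked drops used or supplied for the whole study. Protocol 7.2.3.2 describes discontinuation as leaving the study. No visible text describes stopping study treatment while staying in follow-up. The intercurrent-event lists that might do so (SAP 2.1 and 5.6) are not shown in the public copy. A single case could be far out: stopping drops at day 91 and staying to day 1095 gives 1096 days against 92, a ratio of 11.9. Nothing in the documents says how often that happens, if at all. As planned, surgery to exit is the treatment period.

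**The case for a change.** The strongest case for a change is that a pre-specified rule should yield a value for the subjects it is meant to describe, and this one, taken literally, omits everyone still in follow-up at the primary lock, a group the SAP itself anticipates. One sentence would close the gap using dates already collected, and writing it before the lock would prevent any suggestion of a choice made with treatment codes in hand. The gap does not depend on the label argument, and it is real.

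The observation stands, but its consequence is slight. The Introduction does not assign individual tables to locks, so running this one at Month 12 is likely but inferred. At Month 36, completers should have exit dates and early terminations have the fallback. Unmasking follows query resolution and data revision, and nothing shows that the end-date convention would be set after it. Even if it were, a last-visit or cutoff rule applied to all arms offers no way to favour one, and no between-arm distortion has been shown.

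The elution point does not hold as a criticism of 7.1.1. The 300-subject target in SAP 2.4 belongs to the clinical program. The protocol Synopsis describes that program as including a second pivotal trial, and also cites about 100 implant subjects from a Phase 2 study. The exposure table does not claim to measure elution or to demonstrate the target.

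**Conclusion.** No change to the plan follows. The end date for continuing subjects is a missing detail of the kind analysts routinely settle in shells or programming specifications. It affects one descriptive safety table and its listing. Efficacy results, type I error, adverse event percentages and sample size do not use the variable. The error of −305 to +114 days belongs to a table that would not be issued in that form. The practical difference, last visit against data cutoff, is about 17 to 41 days in a descriptive mean. All these figures rest on assumed accrual and dropout, and the 17 to 41 days also assumes that the Month 12 analysis uses all follow-up to a calendar cutoff. The documents give none of these.

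The double name is a slip of wording. By design the treatment period and the study period coincide, so either name describes the same interval for a subject treated as planned. How many subjects depart from that cannot be determined from the visible text.

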7.1.2. Adverse Events

All adverse event (AE) summaries will be restricted to Treatment Emergent Adverse Events (TEAE), which are defined as those AEs that occurred on/after the initial treatment at Visit 3. Verbatim terms reported by the study sites will be mapped to system organ classes (SOC) and preferred terms assigned using MedDRA (Medical Dictionary for Regulatory Activities) for summary purposes. The adverse event listings will be displayed by treatment group. The number and of percentage subjects experiencing a particular event will be presented.

For a given AE and subject, if more than 1 severity grade is reported, the highest severity grade will be used for analysis.

If a subject experienced more than 1 relationship within an AE, the subject is counted once under maximum relationship. AEs with a missing relationship will be considered related for this summary; events classified as 'Possibly Related', 'Probably Related' or 'Definitely Related' from eCRF will be considered 'Related'; and events classified as 'Unlikely Related', 'Definitely Unrelated' from eCRF will be considered 'Unrelated'.

Adverse events will be classified into ocular AEs and non-ocular/non-study eye AEs. An ocular AE will be determined as indicated on the AE form of eCRF for the study eye only; a non-ocular/non-study eye AEs will include AEs with primary SOCs of eyes for non-study eye and AEs with primary SOCs not for eye.

All TEAEs, ocular TEAEs and non-ocular/non-study eye TEAEs will be summarized by treatment group separately in the following tables:

- Summary of adverse events
- TEAE by SOC and preferred term
- TEAE by SOC, preferred term and maximum severity.
- TEAE by SOC, preferred term and relationship (Related/Not Related) to study treatment.
- Serious TEAEs by SOC and preferred term.
- Ocular TEAEs by preferred term.

The TEAE listings will be prepared, sorted chronologically within subjects for the following types of AEs. Each listing will be displayed by treatment group.

- All AEs
- Serious AEs
- TEAEs leading to death
- TEAEs leading to withdrawal

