### Key Safety Measures

- Intra-operative Adverse events
- Post-operative Adverse events
- Corrected visual acuity (logMAR score using ETDRS chart)
- Slit-lamp biomicroscopy findings
- Gonioscopy findings
- Specular microscopy (at selected sites)
- Ophthalmoscopy findings
- Visual field evaluation

Specified Plan for Data Analysis: Yes (refer to Statistical Section, Section 9)

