### STUDY VARIABLES AND STATISTICAL ANALYSIS

### Efficacy Variable

The primary efficacy variable will be change from baseline IOP in the study eye at each diurnal timepoint specified below.

Safety Variables

Adverse events (intra-operative and post-operative [TEAEs]) in the study will be monitored and summarized.

Ocular safety variables, i.e., best spectacle corrected visual acuity, biomicroscopy findings, gonioscopy findings, specular microscopy findings (at selected sites), ophthalmoscopy findings (including cup-to-disc ratio), and visual field evaluation, will be summarized. In addition, changes from Visit 2 (Baseline) in ocular findings (e.g., conjunctival hyperemia, iris changes) will be assessed.

Analysis Populations Refer to Statistical Analysis Section (Section 9).

|                            | CLINICAL PROTOCOL |        |  |
|----------------------------|-------------------|--------|--|
| Date: Phase: Protocol No.: |                   |        |  |
| June 06, 2022              | Phase 3 Study     | GC-010 |  |

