### 5.2 Safety Measures

Ocular safety measures include intra-operative adverse events, post-operative adverse events (TEAEs), corrected visual acuity, slit lamp biomicroscopy findings, gonioscopy findings, specular microscopy findings (at selected

| CLINICAL PROTOCOL |               |               |
|-------------------|---------------|---------------|
| Date:             | Phase:        | Protocol No.: |
| June 06, 2022     | Phase 3 Study | GC-010        |

sites), ophthalmoscopy findings (including cup-to-disc ratio), and visual field evaluation. Note: See APPENDIX A for a schedule of visits and assessments.

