# 9.4.1 ADVERSE EVENTS

Treatment Emergent Adverse Events (TEAE) are defined as those AEs that occurred after the initial treatment at Visit 3 (Operative Day 0). Verbatim terms reported by the study sites will be coded using the Medical Dictionary for Regulatory Activities (MedDRA) nomenclature. TEAEs will be summarized for each preferred term by treatment group. Adverse event listings will be displayed by treatment group.

AEs that occur on the date of the procedure are classified on the case report form as either intra-operative or post-operative. Post-operative AEs are considered to be TEAEs. Intra-operative AEs will be tabulated separately.

A line listing of serious adverse events will be provided by subject.

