# 10 ADVERSE EVENTS

An Adverse Event (AE) is defined as any untoward and unintended medical occurrence (e.g., sign, symptom, disease, syndrome, intercurrent illness) that occurs in a study subject, regardless of the suspected cause during the study. Adverse events will be clearly documented on the study source document and monitored throughout the course of the study.

Events occurring after signing the informed consent but prior to the implant or sham procedure should be documented in the medical history. Events observed during or after the implant or sham procedure until the final study visit, are to be recorded as AEs.

Any clinically significant change in a subject's condition after receiving any of the study treatments, regardless of causality, is to be considered an adverse event, unless the change is determined to be a continuation of a pre-existing condition that is documented in the subject's medical history. If an adverse event occurs, an AE form must be completed.

An AE includes any of the following:

- An exacerbation or an unexpected increase in frequency or intensity of a pre-existing condition, including intermittent or episodic conditions
- New conditions or illnesses detected or diagnosed after the implant or sham procedure
- A suspected interaction with any of the study treatments
- Signs, symptoms, or the clinical sequelae of a suspected overdose of either any of the study treatments or a concomitant medication
- Any clinically significant laboratory finding that was not present prior to receiving any of the study treatments

An AE does NOT include any of the following:

- Anticipated day-to-day fluctuations of any pre-existing conditions, including the disease under study (OAG and OHT).
- Medical or surgical procedure, (e.g., colonoscopy or hernia repair). The condition that led to the procedure may be an AE, if not present in medical history.
- Hospitalizations where an untoward medical occurrence did not occur (social or convenience admission to the hospital).
- Pre-existing conditions or diseases that were present before receiving any of the study treatments that do not worsen or that are chronic but stable
- Changes in a chronic condition or disease that are consistent with natural disease progression. (These medical conditions should be adequately documented).
- Lack of efficacy of the study treatment for the condition being investigated.

|               | CLINICAL PROTOCOL |               |

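### The SAP restricts all adverse event summaries to a wider TEAE definition than the protocol's and omits the separate intra-operative table that the protocol promises

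*SAP*

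**What the plan says.** Protocol 9.4.1 defines TEAEs as "those AEs that occurred after the initial treatment at Visit 3 (Operative Day 0"). For the day of surgery it adds a second rule: "AEs that occur on the date of the procedure are classified on the case report form as either intra-operative or post-operative". It then assigns the two classes: "Post-operative AEs are considered to be TEAEs. Intra-operative AEs will be tabulated separately".

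The rest of the protocol keeps the same split. The synopsis lists "Intra-operative Adverse events" as a key safety measure in its own right, and under Safety Variables it says "Adverse events (intra-operative and post-operative [TEAEs]) in the study will be monitored and summarized". Section 5.2 reads "Ocular safety measures include intra-operative adverse events, post-operative adverse events (TEAEs), corrected visual acuity". In both of these places the TEAE label is attached to post-operative events only.

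SAP 7.1.2 says: "All adverse event (AE) summaries will be restricted to Treatment Emergent Adverse Events (TEAE), which are defined as those AEs that occurred on/after". As in the protocol, the reference point is treatment at Visit 3. It then lists six tables: an overall summary; TEAEs by SOC and preferred term; the same by maximum severity; the same by relationship; serious TEAEs; and ocular TEAEs by preferred term. Four listings follow: all AEs, serious AEs, events leading to death and events leading to withdrawal. Intra-operative events are not mentioned here or anywhere else in the visible SAP.

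**The concern.** The two documents define TEAEs differently, and only one of them provides for intra-operative events as a separate output. Because the SAP declares that its definitions override the protocol's, a programmer would follow SAP 7.1.2.

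Operative exposure is not the same across arms. Implant subjects have an intraocular implantation, with anaesthesia that may range from topical to general. Control subjects have a sham procedure with a needleless syringe under topical anaesthesia only (Protocol 6.1 and 7.3.5.1). Intra-operative events can occur in any arm but would be expected mainly in the implant arms. Pooling them with later events mixes the risk of the procedure with up to three years of exposure to the implant and drops. A reader of the TEAE tables could not tell which part of a difference between arms comes from surgery and which from the product in use. Safety is a study objective and tolerability one of the two clinical hypotheses, and both are judged from these descriptive tables.

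**Working it through.** The point rests mainly on comparing the texts; the plan gives no figure to reproduce.

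| Item | Protocol 9.4.1 | SAP 7.1.2 |
|---|---|---|
| Start of the TEAE window | After the Visit 3 treatment | On or after the Visit 3 treatment |
| Events on the day of surgery | Split by a CRF flag; post-operative ones are TEAEs | No reference to the flag |
| Intra-operative events | Separate tabulation | No table listed (0 of 6) and no dedicated listing (0 of 4) |
| Scope of AE summaries | TEAEs, plus the intra-operative tabulation | TEAEs only |

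**Step 1: are intra-operative events AEs at all?** Yes. Protocol Section 10 says "Events observed during or after the implant or sham procedure until the final study visit, are to be recorded as AEs".

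**Step 2: which document governs?** SAP Section 1 states that the SAP's statistical definitions and methods take precedence over the protocol's.

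**Step 3: where do intra-operative events go under the SAP?** There are two readings.

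- *The procedure is the initial treatment.* An event during it occurs on treatment and counts as a TEAE. It enters all the TEAE rates and no listed table separates it. This is the more natural reading. SAP 4.4.2 supports it, since it uses complete dates to decide whether an AE falls within treatment.
- *Treatment starts only once the procedure is finished.* Intra-operative events are then not TEAEs, and the restriction to TEAEs removes them from every summary table. They should still appear in the listing of all AEs, but a listing is not a tabulation by arm.

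On either reading, the table promised in Protocol 9.4.1 is missing from the SAP's list.

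**Step 4: scope.** The inputs are about 558 subjects randomised 1:1:1, or about 186 per arm (protocol synopsis).

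- Subjects assigned to implantation: 2 × 186 = 372, and 372 / 558 = 66.7%. The other 186 are assigned to sham.
- Shift in one arm's rate for one preferred term, per subject whose only event of that term is intra-operative: 1 / 186 = 0.54 percentage points.

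The second figure is a unit of sensitivity and not an estimate of the effect, because the documents give no intra-operative event rate. The actual denominator will be the safety set grouped by treatment received, which may differ slightly from 186.

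**The case against.** The strongest reply is that the material that could settle the matter is not visible. The change table in SAP Section 9 shows an item number but no content, and the table shells are a separate document. The departure may be declared in the first and the table may exist in the second. This stands as a limit: it cannot be said that the change is undeclared or that no table is planned. It does not remove the conflict in SAP 7.1.2 itself, which restricts every AE summary to TEAEs and does not say whether intra-operative events belong to them.

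A second reply is that the conflict is thin. The protocol never says outright that intra-operative events are not TEAEs. If the SAP makes them TEAEs, a separate table would simply be a subset, and the SAP does not expressly withdraw it. This is partly right: exclusion is an inference. It is a firm one, however, because the synopsis and Section 5.2 attach the label to post-operative events only, and Section 9.4.1 gives the other class its own output.

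A third reply is that including the events hides no harm. If they occur mainly in the implant arms, implant rates go up. That is fair on the natural reading. The loss is in interpretation, because procedural risk and later risk can no longer be told apart. The reading on which events drop out of the summaries is the less likely one and should carry less weight.

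Finally, safety is descriptive only (Protocol 9.4) and the split can be rebuilt from the CRF. Both points are correct, and they limit how serious the problem is.

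**Conclusion.** The concern holds for the visible text. Protocol and SAP state different TEAE rules, the SAP's rule prevails, and the SAP lists no table for an outcome that the protocol names as a key safety measure. The implant-arm TEAE rates therefore depend on which document is followed, by 0.54 percentage points per affected subject per term at 186 per arm. The total effect cannot be quantified without an intra-operative event rate. No error rate, power or efficacy conclusion changes. The conclusion assumes that neither the hidden content of SAP Section 9 nor the separate shells resolve the point; even if they do, the wording of SAP 7.1.2 should be brought into line with Protocol 9.4.1. This should be corrected before the analysis but does not threaten the trial's main result.

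**What to change.** In SAP 7.1.2, adopt the protocol's rule. For AEs dated on the day of surgery, use the existing CRF classification and count the post-operative ones as TEAEs. Count all AEs on later days as TEAEs. Add one table of intra-operative AEs by treatment group in the safety set, and word the restriction on AE summaries so that it permits this table.

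If the intention is to count intra-operative events as TEAEs, say so in 7.1.2, record the change and its reason in SAP Section 9, and either keep the separate table or state that it is withdrawn.

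The cost is a few sentences and one table. No new data are needed: Protocol 9.4.1 places the classification on the CRF, and Protocol 7.3.5.1 already has intra-operative events noted on the Operative Day 0 form.
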